Hypothesis 1. Using intent to treat principles, we will test for differences between the intervention and usual care groups on physical activity at the 3 month assessment. We will assess the intervention effect size of change in physical activity from baseline testing to 3 months using an ANCOVA model with adjustment for age; covariates from Table 10 (e.g., cognitive processing speed); and each participant's baseline score. Adjustment for baseline score is useful in this relatively small RCT to eliminate any potential baseline differences between groups that may occur despite the randomization procedure. We expect that the mean physical activity at 3 months will be significantly higher in the intervention group than in the usual care control group. Every attempt will be made to ensure high retention rates at posttest, although some attrition is to be expected. The level and patterns of missing data will be evaluated relative to intervention condition and other baseline characteristics to determine whether there is systematic bias in the missing data. If necessary and appropriate, based on the level and patterns of missing data, state-of-the-art techniques (e.g., multiple imputation) will be used.

Aim 1 secondary outcomes. The analyses for Aim 1 secondary outcomes will be used to detect trends and to provide necessary data to calculate the sample size needed to detect differences in a larger RCT. We will assess the intervention effect size by calculating a Cohen's d effect size comparing the means of the two groups at the three-month follow-up. We will use separate ANCOVA models to assess pre-post intervention changes in the following outcomes listed in Table 10: physical function by 400-meter rapid gait speed (differentiates adults with higher baseline function); Short Physical Performance Battery (differentiates adults with lower baseline function); intermediate physical activity behavioral constructs from SCT; intermediate functional outcome (lower extremity strength); and metabolic outcome (Hemoglobin A1c).

Table 10. Outcome, Predictor, and Covariate Measures for [name] K23

Outcome	Instrument	Variable	Measure
Physical Activity outcomes			

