Objective physical activity	Actigraph GT3x+ accelerometer measures physical activity objectively as minutes/week of moderate intensity and vigorous intensity physical activity, respectively. ⁸⁰ We define moderate intensity levels by the methods of Freedson et al. ⁸¹ Participants will wear the Actigraph for a 7-day period pre/post intervention. We will ensure measurement during a typical 7-day period and will use standard wear-time validation procedures to ensure valid weekday and weekend data. Actigraph data will be collected on the 7 days between physical function and VO ₂ max testing.	Continuous	Aim 1 1° outcome
Physical activity behavioral constructs from SCT	Standard survey measures to assess the following physical activity behavior assessments of constructs from SCT: Self-efficacy to do physical activity of increasing duration; ^{82,83} Social-environmental support is a valid measure of how others support one's healthy lifestyle choices; ⁸⁴ Lower barrier scores on the Dishman physical activity barriers survey are associated with higher levels of physical activity; ⁷⁷ Physical Activity outcome expectancy for elders survey includes positive elements of physical activity for older adults, including health-related factors – better scores are associated with higher physical activity levels ⁸⁵	Continuous	Aim 1 Predictor variable: physical activity (PA predictor)
Physical Function outcomes			
Cardiorespiratory fitness (VO ₂ max)	To assess cardiorespiratory fitness, we measure breath-by-breath utilization of oxygen (VO ₂) and carbon dioxide (VCO ₂) with a Medgraphics Ultima CPX metabolic cart (Minneapolis, MN). We also measure blood pressure (auscultation), and cardiac status (12-lead ECG). To determine VO ₂ max, subjects perform treadmill exercise to exhaustion using a standard protocol. ^{86,87} We define VO ₂ max per standard practice. ⁸⁶	Continuous	Aim 1 2° outcome
Physical function	400-meter rapid gait speed test measures fitness and mobility; it is sensitive to change for adults with minimal to mild functional impairment ; predicts disability and mortality. ⁸⁸ Physical function measures will be assessed on a separate study date from the VO ₂ max testing.	Continuous	Aim 1 2° outcome

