Physical function	The Short Physical Performance Battery (SPPB) measures function with the following valid subscales: balance, usual walking speed, and repeated chair rise. The SPPB is sensitive to change for adults with moderate to severe functional impairment , and predicts disability and mortality. ^{68,89}	Ordinal, range 0-12	Aim 1 2° outcome
Lower extremity strength	Lower extremity strength will be measured as leg extensor (quadriceps) and leg flexor (hamstring) strength using [name] laboratory's established techniques. ^{38,90}	Continuous	Aim 1 Function predictor
Grip strength	Hand grip strength will be measured by dynamometer. ⁹¹	Continuous	Aim 1 2° outcome
Metabolic control outcome			
Hemoglobin A1c	Average glycemic control measured by standard methods ⁹²	Continuous	Aim 1
Covariates for adjustment			
Depression symptoms	Center for Epidemiologic Studies Depression Scale measures depressive affect severity and is valid in people with ^{93,94} and without T2D. ^{95,96}	Continuous	Aim 1 covariate for adjustment
Lower extremity arthritis pain symptoms	Western Ontario and McMaster Universities Arthritis Index—valid measure of knee and hip pain and stiffness. ⁹⁷	Continuous	Aim 1 covariate
Cognitive processing speed	Stroop test –measures cognitive processing speed as a valid predictor of cognitive function in adults with and without T2D. ⁹⁸⁻¹⁰⁰	Continuous	Aim 1 covariate

DEXA scan	DEXA will allow the calculation of body composition as fat-free mass and total mass so that we may report exercise performance levels standardized to these body composition measures.	Continuous	VO ₂ max covariate for adjustment
Cognitive executive function	Behavioral Dyscontrol Scale – valid measure of executive function in adults with and without T2D. ^{101,102}	Continuous	Aim 1 covariate
Process outcomes			
Acceptability	Percent of intervention patients who would recommend intervention ¹⁰³ ; Percent of clinical providers/staff who recommend continuing to offer the intervention to patients ¹⁰³	Percentile	Aim 2
Time burden	Patient time required for each intervention visit ¹⁰³ ; Staff/provider time required for each intervention visit ¹⁰³	Continuous	Aim 2
Safety outcomes			
	Participant report of outcomes after baseline testing: falls, musculoskeletal injuries, foot ulcers, hypoglycemia ^{20,24,57}	Continuous	Safety

12.3k. ANALYSIS OF ACCEPTABILITY OUTCOMES (Aim 2 and Safety analysis)

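### VO2max and grip strength are Aim 1 secondary outcomes in Table 10 but have no ANCOVA model in 12.3j, so as written their group comparison ignores baseline values

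*Combined protocol and SAP*

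**What the plan says.** All of this is in section 12.3 of the combined protocol and SAP.

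- **Table 10, VO2max row.** Labelled an Aim 1 secondary outcome, under the physical function heading. It is measured by a maximal test: "subjects perform treadmill exercise to exhaustion using a standard protocol".
- **Table 10, grip strength row.** Same label, same heading: "Hand grip strength will be measured by dynamometer".
- **Table 10, DEXA row.** Labelled an adjustment covariate for VO2max. Its purpose is to "report exercise performance levels standardized to these body composition measures"; the measures are fat-free mass and total mass.
- **12.3j, paragraph on Aim 1 secondary outcomes.** It opens with the class as a whole: "The analyses for Aim 1 secondary outcomes will be used to detect trends" and to size a larger trial. It then plans a Cohen's d "comparing the means of the two groups at the three-month follow-up". Next comes the model sentence: "We will use separate ANCOVA models to assess pre-post intervention changes in the following outcomes listed in Table 10". Its list starts "in the following outcomes listed in Table 10: physical function by 400-meter rapid gait speed" and ends "intermediate functional outcome (lower extremity strength); and metabolic outcome (Hemoglobin A1c". Between these stand the SPPB and the SCT constructs. VO2max and grip strength do not appear.
- **12.3j, power and data-analysis paragraphs.** These foresee effect-size estimates for physical function outcomes under Aim 1b, and descriptive summaries of every outcome and covariate.

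**The concern.** Two outcomes in the same tier as the walk and the SPPB are treated differently, and no reason is given. The list does not look like a set of examples. It is introduced as the outcomes that follow, it closes with a final conjunction, and the preceding paragraph uses e.g. where examples are meant. Nor is it shorthand for the secondary tier, because three of its five entries carry other labels in Table 10.

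Two things are at stake:

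- **Precision.** The Hypothesis 1 paragraph argues for baseline adjustment because the trial is relatively small. That argument applies equally to VO2max and grip strength, but the only comparison that reaches them uses follow-up means alone.
- **Analytic freedom.** With a d in the text and a covariate in Table 10 that implies a model, an analyst could report either one after seeing both. For VO2max the DEXA row adds a further open choice between fat-free mass and total mass, and between a covariate (the label) and a standardised value (the description).

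**Working it through.** **Step 1: the two lists side by side**

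| Measure | Label in Table 10 | In the 12.3j ANCOVA list? |
|---|---|---|
| 400-metre walk | Aim 1 secondary | Yes |
| SPPB | Aim 1 secondary | Yes |
| VO2max | Aim 1 secondary | **No** |
| Grip strength | Aim 1 secondary | **No** |
| SCT constructs | Predictor of physical activity | Yes |
| Lower extremity strength | Function predictor | Yes |
| Hemoglobin A1c | Aim 1, no tier given | Yes |

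Two of the four labelled secondary outcomes have no model. Three measures without that label have one.

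**Step 2: what VO2max and grip strength do receive**

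- Descriptive summaries, which cover all outcomes.
- Cohen's d on three-month means. That sentence precedes the list, is not limited to it, and speaks of Aim 1 secondary outcomes as a class. Formula: d = (mean at exit, intervention − mean at exit, usual care) / SD. No baseline term appears.
- For VO2max, a DEXA covariate. A covariate needs a model, and 12.3j states none for VO2max.

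**Step 3: the plan's own figures, to see whether they move**

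Inputs from 12.3j: d = 0.61, two-sided alpha 0.05, n = 90, so 45 per arm at 1:1.

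- Noncentrality: 0.61 × √(45/2) = 2.89.
- Power: Φ(2.89 − 1.96) = 82.5%, or 81.6% with the noncentral t. Both agree with the stated figure of over 80%.
- Enrolment: 90 / 0.70 = 128.6, so 129; and 130 × 0.70 = 91. Both agree with 130 enrolled.

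These concern physical activity only. Nothing in this point changes them.

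**Step 4: size of the precision loss**

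The documents give no baseline-to-exit correlation ρ for either outcome, so ρ is an assumption, shown over a range. In SD units, ignoring the small terms for estimating the SD and the covariate slope:

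- Follow-up means only: half-width = 1.96 × √(2/45) = 1.96 × 0.211 = 0.41 SD.
- Own-baseline ANCOVA: the variance is multiplied by 1 − ρ², and the half-width by √(1 − ρ²).

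| Assumed ρ | 1 − ρ² | 95% half-width (SD) |
|---|---|---|
| 0 (no adjustment) | 1.00 | 0.41 |
| 0.5 | 0.75 | 0.36 |
| 0.7 | 0.51 | 0.30 |
| 0.9 | 0.19 | 0.18 |

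**Step 5: are baseline values collected?**

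Section 12.3a places outcome measurement at baseline and three months. Table 8 has outcome testing at visits 2-3 and 10-11. The accelerometer row in Table 10 sets a pre and post wear week between function testing and VO2max testing. Baseline values are therefore a sound inference, although no visit row names the treadmill test or the dynamometer.

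**The case against.** The strongest reply is that both outcomes are already prespecified and already compared. Table 10 names them, and the Cohen's d sentence covers the secondary tier and is a between-group comparison. The Aim 1b statement on effect-size estimates covers physical function, the Table 10 heading under which both sit. The DEXA row shows that adjusted or standardised VO2max reporting was foreseen. Secondary analyses are meant only to detect trends and to size a later trial. Hypothesis 1 speaks of physical activity and physical function without naming fitness.

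Most of this stands, and it rules out a stronger reading. A reader might infer from the omission that the maximal treadmill tests feed no planned comparison or analysis. With up to 130 baseline and 91 exit tests (130 + 0.7 × 130 = 221, if everyone enrolled and everyone retained is tested), that would be a serious charge. The documents do not support it: the d and the descriptive summaries are planned, and 221 counts procedures, not statistical impact. Nor do they support the inference that the outcomes could only be analysed outside the plan. Naming them in Table 10 limits selective choice of outcome; what remains is choice of analysis.

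The reply does not explain why two outcomes of one tier get a model and the other two do not. It also leaves the DEXA covariate without a model. A plan meant to supply effect sizes for a later trial benefits directly from estimating them more precisely.

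**Conclusion.** The point holds in a limited form. Table 10 and 12.3j disagree: VO2max and grip strength are secondary outcomes with no specified ANCOVA. As written they receive descriptive summaries and an unadjusted d at three months, and the DEXA adjustment of VO2max has no stated model.

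The consequences are less precise estimates than for the walk and the SPPB, and an open choice between unadjusted and adjusted results. At assumed correlations of 0.5 to 0.9, adjustment would remove 25% to 81% of the variance (ρ² = 0.25 to 0.81).

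This rests on three readings: the ANCOVA list is closed; the secondary models adjust for own baseline as the Hypothesis 1 model does (the secondary paragraph does not repeat the covariates); and both outcomes are measured at baseline. The primary analysis, power and sample size do not change. Severity is minor; this is a free improvement.

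**What to change.** In the secondary-outcomes paragraph of 12.3j:

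1. Add cardiorespiratory fitness (VO2max) and grip strength to the list of ANCOVA models.
2. State that each is adjusted for its own baseline value and reported as an adjusted group difference with a 95% CI.
3. State how DEXA enters the VO2max model: which measure (fat-free mass or total mass), at which time point, and whether as a covariate or by standardising the outcome. A baseline value is safer as a covariate, since the exit value could itself be affected by the intervention.

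If no model is intended for these two outcomes, relabel them in Table 10 as descriptive and amend the DEXA row to match. In either case, reconcile the two places before any exit data are seen.

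The cost is a line or two of text and two more models on data already being collected. No new visits, tests or participants are needed.

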12. RESEARCH STRATEGY

12.1 SIGNIFICANCE

12.1.1. Ongoing Importance of physical activity for CV disease prevention in T2D The prevalence of diabetes mellitus has more than tripled in the past 30 years, and currently affects 25.8 million Americans.⁶ T2D accounts for >90% of prevalent diabetes cases in adults.⁷ Because people with T2D are at very high risk for CV disease, people with T2D are a high priority NHLBI study population.⁸⁻¹¹ Several large observational studies support regular physical activity as a potent therapy to reduce CV mortality in people with T2D.¹²⁻¹⁵ A recent meta-analysis of prospective cohort studies found improved CV outcomes in participants with diabetes by physical activity strata (HR = 0.61 (0.47-0.80) for CV mortality for highest vs. lowest physical activity levels).¹⁶ Data from RCTs have been mixed, as lower stroke event rates (HR = 0.62 (0.35-0.98) were observed in the intervention vs. placebo group of an RCT of a behavioral intervention that increased physical activity¹⁷, but the Look AHEAD study was stopped for lack of group differences in CV outcomes¹⁸. Lower than expected CV outcomes in both Look AHEAD

study groups may have under-powered this study to detect an intervention effect.¹⁸

[figure not shown]
Overall, the consistent benefits of regular physical activity with regard to cardiorespiratory fitness, CV mortality, and all-cause mortality that have been observed in large cohort studies provide a convincing evidence base that regular physical activity improves CV health. Also, one study found mean annual health costs were ~\$2000 less in people with T2D who performed physical activity ≥ 2 times/week vs. <1 time/week.¹⁹ Thus, regular physical activity, a critical cornerstone of T2D treatment, may actually generate cost savings.²⁰

12.1.2. Why improve function? PFLs predict disability, loss of independence, and premature mortality for adults.²¹⁻²³ Regular physical activity can preserve function and reduce these adverse outcomes.²⁴⁻²⁷

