Overcome barriers: Rather than suggesting solutions, counselor invites participant to solve the barriers to activity he/she identified. Counselor adds advice on time management strategies.
Tracking: Participant records daily type and times of activity K23 Optimization: Wearable device simplifies ability to track activity

consent, participants will undergo 1:1 patient-level randomization to the intervention or usual care group. (Figure 5)

Study Settings: Enrollment (V1), Baseline testing (V2-3), and Exit testing (V10-11) will be conducted in the CCTSI outpatient Clinical Translational Research Center.

12.3f. INTERVENTION GROUP

Figure 5. [name] NIDDK K23 Study Flow

The proposed intervention is based on SCT (Figure 4 in “Significance”) and seeks to increase physical activity and improve strength by addressing individual, behavioral, and social/environmental factors. The health promotion clinic staff will deliver counseling by phone on a bi-weekly basis — a clinic physician assistant will coordinate with the counselor during in-person clinic visits (Figure 3 and Table 8), teach participants to perform strengthening exercises; and assess for safety concerns, such as hypoglycemia. We optimized the existing VA LIFE intervention in our funded CU LIFE pilot, by simplifying the VA LIFE counseling guide for delivery as brief, tailored counseling by health promotion clinic staff (see Appendix), and by adding strengthening exercises that engage multiple muscles (see Appendix). To ensure the intervention is brief enough for clinical use and to incorporate T2D-specific barriers and facilitators, we will make further adaptations in the pre-RCT Adaptation phase, as described above in 12.3b.

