Safety analysis: For ethical reasons, in addition to the acceptability outcomes addressed in Aim 2, we will monitor for study group differences in safety-related outcomes, in order to assess for any potential study harm. We selected the following safety outcomes based on relevant use in prior trials and per expert description of safety concerns in T2D; falls, musculoskeletal injuries, severe hypoglycemia (glucose <60 mg/dl or hospitalization/Emergency department visit for hypoglycemia).^{20,24,57} At study exit visit 9, we will ask participants if any of the following safety-related outcomes occurred since baseline testing was completed in visit 2: fall requiring clinical evaluation; fall that did not require clinical evaluation; musculoskeletal injury requiring clinical evaluation; musculoskeletal injury that did not require clinical evaluation; severe hypoglycemia (glucose <60 mg/dl or clinical evaluation for hypoglycemia), foot ulceration. For each safety outcome measured, we will descriptively report these as both dichotomous outcomes (Yes/No) as well as the frequency of safety events (e.g., number of hypoglycemic episodes). We will use ANCOVA to obtain preliminary data on the group differences in safety outcomes with adjustment for baseline conditions that may increase safety risk. Baseline conditions that may increase safety risk include the following: baseline moderate-to-severe impairment on SPPB (baseline score <10), prior history of fall, slowed cognitive processing speed).

12.3l POTENTIAL PROBLEMS AND ALTERNATIVE STRATEGIES We have planned alternatives for potential problems that may arise. For example, if participants report new medical concerns or symptoms during the telephone counseling sessions with the health promotion clinical staff, staff members will transfer the patient to the clinic triage nurse to evaluate the patient's symptoms. Also, if participants report new musculoskeletal pains to the health promotion clinic staff, the staff member will send an electronic health record note to the physician assistant conducting the in-person treatment visits to advise the patient on any recommended treatment or activity restrictions.

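### The 12.3k safety list has no cardiovascular or all-cause serious-event item, and its visit numbers conflict with the schedule, leaving the exit treadmill test outside the recall window on a literal reading

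*Combined protocol and SAP*

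**What the plan says.** Section 12.3k states that the safety analysis is meant to pick up possible harm from the study. It chooses its outcomes from earlier trials and expert opinion on hazards in type 2 diabetes, and names them as "falls, musculoskeletal injuries, severe hypoglycemia (glucose <60 mg/dl or hospitalization/Emergency department visit for hypoglycemia". The exit questions in the same section are six items on four kinds of event: falls (with and without clinical evaluation), musculoskeletal injuries (with and without), severe hypoglycemia, and foot ulceration. Table 10 gives the same four: "Participant report of outcomes after baseline testing: falls, musculoskeletal injuries, foot ulcers, hypoglycemia".

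On timing, 12.3k says "At study exit visit 9, we will ask participants if any of the following safety-related outcomes" "occurred since baseline testing was completed in visit 2". Section 12.3e says "Enrollment (V1), Baseline testing (V2-3), and Exit testing (V10-11) will be conducted" at the research center. Table 8 agrees, and makes visit 9 a phone counseling contact in the intervention arm and a print mailing in usual care.

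On risk and testing, 12.1.1 says "Because people with T2D are at very high risk for CV disease", and the VO2max row of Table 10 says "subjects perform treadmill exercise to exhaustion using a standard protocol". That row adds "We also measure blood pressure (auscultation), and cardiac status (12-lead ECG" and classes VO2max as an Aim 1 secondary outcome. Section 12.3a has outcomes measured at baseline and at 3 months.

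**The concern.** The purpose given in 12.3k is broad, but the list is narrow and closed. It has no open question for any other event. Emergency or hospital care is named only for hypoglycemia, and clinical evaluation only for falls, musculoskeletal injury and hypoglycemia. A participant admitted with angina would answer no to every question. A collapse of cardiac origin would count, at most, as a fall, without its cause.

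This matters because sedentary adults aged 50-85 are encouraged toward more activity on their own and take treadmill tests to exhaustion. Section 11 presents enhanced safety as a main advantage of the design, and 12.1.4 looks ahead to use in other clinics. A clean 12.3k result would be silent on cardiovascular and all-cause serious events, and a reader could take that silence for absence.

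The visit numbers add a second gap. If the questions really are asked at visit 9, they come before exit testing. They also fall at a contact that, for usual care, is only a mailing.

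**Working it through.** The documents give no figure for safety events, so the check is mainly a comparison of passages, with arithmetic for scale.

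**1. The plan's own numbers.** Section 12.3j enrolls 130, allows up to 30% attrition and powers on 90. Check: 130 x 0.70 = 91, which agrees with 90 (45 per arm). At full enrollment, 1:1 allocation gives 65 per arm.

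**2. The lists.**

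| Event | 12.3k exit questions | Table 10 |
|---|---|---|
| Fall | yes | yes |
| Musculoskeletal injury | yes | yes |
| Hypoglycemia | yes (severe) | yes |
| Foot ulcer | yes | yes |
| Cardiovascular event or symptom | no | no |
| Emergency visit or hospitalization, any cause | no | no |
| Death | no | no |

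Two other sources of information exist: the ECG during the VO2max test, and symptoms reported by phone and passed to the triage nurse (12.3l). No text carries either into the 12.3k analysis.

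**3. Number of maximal tests.** Assume every enrolled participant takes the baseline test and every completer the exit test.
- No attrition: 130 x 2 = 260.
- 30% attrition: 130 + 91 = 221.

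**4. The window.**

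| | 12.3k | 12.3e and Table 8 |
|---|---|---|
| Baseline testing | completed in visit 2 | visits 2-3 |
| Exit | visit 9 | visits 10-11 |
| Visit 9 | exit visit where questions are asked | phone call (intervention) or mailing (usual care) |

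Read literally, questions at visit 9 precede the exit treadmill test, so an event at that test is not asked about. The start is ambiguous. Table 10 puts function testing and VO2max on separate dates with the 7 accelerometer days between them, and no visit number is assigned to VO2max. If it is at visit 3 and the window opens at visit 2, the baseline test is inside.

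**5. What added items could show.** With zero events in n participants, the one-sided 95% upper limit is 1 - 0.05^(1/n).
- n = 65: 4.5%.
- n = 45: 6.4%.

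These are limits over about 12 weeks. At a constant rate, 4.5% annualizes to 1 - (1 - 0.045)^(52/12), about 18%.

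**6. Expected counts.** The documents give no cardiovascular event rate, so the rates r below are assumptions. The 12-week risk is p = 1 - exp(-r x 12/52). For 130 participants all followed, the expected count is 130p and the chance of at least one event is 1 - (1 - p)^130.

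| Assumed annual rate | Expected events | Chance of at least one |
|---|---|---|
| 1% | 0.3 | 26% |
| 2% | 0.6 | 45% |
| 5% | 1.5 | 78% |
| 10% | 3.0 | 95% |

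Across this range, the counts support a listing, not a comparison of arms.

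**The case against.** The strongest defense is that the list is targeted by design. The plan cites cardiovascular risk as a reason to promote activity. The hazards of activity that it names are mainly balance, cognition, symptoms on walking, hypoglycemia, injury and foot ulcers, and the list largely matches these. Section 12.3k also gives a basis for its choice. This stands in part: a reader might infer that the plan omits the very hazard it stresses most, but that would confuse disease burden with the activity hazards it names. The defense does not explain why an analysis of any possible study harm has no open or all-cause item.

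Three other stronger readings are tempting and are not supported.
- *The baseline maximal test is outside the window by definition.* It may be inside if VO2max is at visit 3, and a delayed consequence of a test at visit 2 would fall after the window opens. Both arms also take this test before any intervention contact, so missing it would hide procedural harm, not a treatment difference.
- *Cardiovascular events will go unrecorded in the trial.* Only their absence from the 12.3k result is shown. The text refers to a section 4 and an Appendix that are not available here, and the exclusion criteria in Table 6 cannot be read. Screening may lower the risk, but it does not count events.
- *Adding the items would establish safety.* A limit of 4.5% or 6.4% over 12 weeks excludes little.

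It is also fair that self-report cannot capture deaths or events in people who miss exit, and that recall may differ when one arm has repeated safety contacts and the other only mailings.

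**Conclusion.** The point holds in two parts. First, the list in 12.3k and Table 10 contains no cardiovascular, all-cause emergency, hospitalization or death item, so following it exactly leaves such events out of the stated safety result. This rests on the text alone. Second, the visit numbers in 12.3k disagree with 12.3e and Table 8 at both ends of the window. The firmer conflict is at exit, where a literal reading excludes the exit maximal test; at baseline the effect is undetermined.

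The exposure is about 221 to 260 maximal tests plus 12 weeks of encouraged activity, assuming VO2max is done at both time points as 12.3a and Table 10 imply. The number of events missed cannot be estimated from the documents. The primary analysis is unaffected. This is a cheap improvement to a descriptive safety report, not a flaw that undermines the trial.

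**What to change.** 1. Add two items to the 12.3k exit questions and to Table 10: a cardiovascular event or symptom, and any emergency visit or hospitalization with its cause. List deaths, and events in participants who do not complete, from sources the study can reach, such as the clinics' electronic health record, not from self-report.
2. Reconcile the visit numbers in 12.3k with 12.3e and Table 8. State which baseline visit opens the window, and which visit VO2max testing belongs to. Ask the questions in both arms at the exit testing visits, including after the last test. List events observed during any maximal test separately.
3. Report these events descriptively by arm, with an upper limit where none occur, and not as a between-arm test.

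Cost: a few more minutes per participant, a brief record check for non-completers, and some unrelated hospitalizations to classify. Because contact is unequal between arms, state possible recall differences as a limitation when symptom counts are reported.
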